8.2.9 Treatment of Overdose

For purposes of this study, an overdose will be defined as any dose of any drug administered as part of the study exceeding the dose prescribed by the protocol. It is up to the PI or the reporting physician to decide whether a dose is to be considered an overdose, in consultation with the Sponsor.

Refer to the IB for specific treatment of overdose. Decisions regarding dose interruptions or modifications will be made by the PI or designee in consultation with the Sponsor Clinical Director based on the clinical evaluation of the participant.

8.3 Pharmacokinetic Assessments

8.3.1 Blood Sampling and Processing

For all participants, blood samples for the determination of MK-8527 and MK-8527-TP will be collected at scheduled time points as delineated in the Schedule of Activities ([Section 1.3](#)).

Instructions for blood sampling, collection, processing, and sample shipment will be provided separately.

The allowed window for PK blood sampling is indicated in [Table 2](#).

Table 2: Window for PK Blood Sample Collection

Nominal Time	Allowed Window
Predose	Within 30 minutes prior to dosing
> 0 to < 1 hour	$\leq \pm 5$ minutes
1 to < 2 hours	$\leq \pm 10$ minutes
2 to < 24 hours	$\leq \pm 15$ minutes
24 to < 48 hours	$\leq \pm 1$ hour
48 to ≤ 168 hours	$\leq \pm 4$ hours
> 168 to < 672 hours	$\leq \pm 24$ hours
≥ 672 hours	$\leq \pm 48$ hours

8.3.2 Plasma and PBMC Pharmacokinetic Parameters

The following PK parameters for plasma MK-8527 and PBMC MK-8527-TP will be calculated, as appropriate:

AUC0-last:	Area under the concentration versus time curve from 0 to the time of the last quantifiable (above lower limit of quantitation) sample
AUC0-inf:	Area under the concentration versus time curve from 0 to infinity after single dosing
AUC%extrap:	Percent of AUC0-inf extrapolated
CL/F:	Apparent clearance (plasma MK-8527 only)
Cmax:	Maximum observed drug concentration after the administration of a given dose
C168:	Drug concentration at Hour 168 (PBMC MK-8527-TP only)
C672:	Drug concentration at Hour 672 (PBMC MK-8527-TP only)
Tmax:	Time to maximum observed drug concentration
λ_z :	Lambda z, Apparent terminal elimination rate constant
$t_{1/2}$:	Apparent terminal half-life
Vz/F:	Apparent volume of distribution during terminal phase (plasma MK-8527 only)

No value for λ_z , AUC0-inf, AUC%extrap, CL/F, Vz/F, or $t_{1/2}$ will be reported for cases that do not exhibit a terminal log-linear phase in the concentration-time profile.

PK parameters will not be calculated for participants with less than 3 consecutive postdose time points with quantifiable concentrations.

8.3.3 Urine Sampling and Processing

Urine for PK assessments will be collected at the specified intervals delineated in the Schedule of Activities ([Section 1.3](#)). Urine samples will be collected per schedule whenever possible, as some participants with RI may not be able to produce urine during each collection interval.

Prior to the predose sample, each participant will be instructed as to urine collection methods. All urine during an interval is to be collected.

On Day 1, a spot collection will be obtained prior to dosing for the predose sample. Participants will be asked again to empty their bladder within approximately 15 minutes prior to dosing, and no urine will be collected at this time unless it is needed for the predose sample. Only one predose urine sample will be collected on Day 1.

Participants will be encouraged to void at the end of each collection interval. If they do void at any time during the collection interval, the time should be documented. Should this be the case, participants need to void again at the end of the collection period, as scheduled. However, should participants be unable to void, this will be documented as well.

Urine will be refrigerated during the collection intervals. At the end of each interval, urine will be pooled and thoroughly mixed. Total urine volume will be weighed and recorded.

Instructions for urine sampling, collection, processing, and sample shipment will be provided separately.

8.3.4 Urine Pharmacokinetic Parameters

The following PK parameters for urine MK-8527 will be calculated, as appropriate:

Ae:	Amount of unchanged drug excreted in urine (cumulative or during a collection interval)
CL _r :	Renal clearance calculated as $Ae(t'-t'')/AUC(t'-t'')$ where $t'-t''$ is the longest interval of time during which Ae and AUC are both obtained
fe:	Fraction (in percentage) of dose excreted in urine

8.3.5 Long Term Storage and Use

Any residual plasma, PBMC, and/or urine from the PK samples will be stored by the Sponsor or bioanalytical facility for up to 15 years after dosing and may be used for future analyses (e.g., PK assessment). Tubes will be identified with a barcode using an appropriate label. No diseases/conditions, deoxyribonucleic acid (DNA), or ribonucleic acid (RNA) will be the focus of these analyses. The analyses will only focus on analytes/biomarkers. Samples will not be submitted to a public database. The Sponsor and contract research organizations involved in the clinical conduct, bioanalytical analyses and PK and statistical analyses of the

data will have access to the samples and/or the data that resulted from the analysis, if performed. By signing the ICF, participants agree to the possible future analysis of these samples. Any additional research on these samples unspecified by this protocol will require approval from the participants.

8.3.6 Analytical Method

Samples from all participants will be assayed even if the participants do not complete the study.

Samples will be analyzed for plasma MK-8527, PBMC MK-8527-TP, and urine MK-8527 using validated bioanalytical methods.

If indicated, these samples may also be measured and/or pooled for assay in an exploratory manner for metabolites and/or additional pharmacodynamic markers.

8.4 Planned Exploratory Biomarker Research

8.4.1 Biomarkers

8.4.1.1 Planned Genetic Analysis

Genetic variation may impact a participant's response to therapy, susceptibility to, severity, and progression of disease. Variable response to therapy may be due to genetic determinants that impact drug absorption, distribution, metabolism, and excretion; mechanism of action of the drug; disease etiology; and/or molecular subtype of the disease being treated. Therefore, where local regulations and IRB allow, a sample will be collected for DNA analysis from consenting participants.

DNA samples may be used for research related to the study drug(s), the disease under study, or related diseases. They may also be used to develop tests/assays including diagnostic tests related to the disease under study, related diseases, and study drug(s). Genetic research may consist of the analysis of 1 or more candidate genes, the analysis of genetic markers throughout the genome, or analysis of the entire genome. Analysis may be conducted if it is hypothesized that this may help further understand the clinical data.

The samples may be analyzed as part of a multistudy assessment of genetic factors involved in the response to understand study disease or related conditions.

8.4.1.1.1 Planned Genetic Analysis Sample Collection

The planned genetic analysis sample should be collected for planned analysis of the association between genetic variants in DNA and drug response. This sample will not be collected at the site if there is either a local law or regulation prohibiting collection, or if the IRB does not approve the collection of the sample for these purposes. If the sample is collected, leftover extracted DNA will be stored for FBR if the participant provides

documented informed consent for FBR. If the planned genetic analysis is not approved, but FBR is approved, this sample will be collected for the purpose of FBR.

The planned genetic analysis sample should be obtained predose on Day 1, but may be collected at the next scheduled blood draw, if needed. Sample collection, storage, and shipment instructions for planned genetic analysis samples will be in the operations/laboratory manual.

8.4.2 Future Biomedical Research

The Sponsor will conduct FBR on DNA specimens for which consent was provided during this clinical study.

Such research is for biomarker testing to address emergent questions not described elsewhere in the protocol and will only be conducted on specimens from appropriately consented participants. The objective of collecting/retaining specimens for FBR is to explore and identify biomarkers that inform the scientific understanding of diseases and/or their therapeutic treatments. The overarching goal is to use such information to develop safer, more effective drugs/vaccines, and/or to ensure participants receive the correct dose of the correct drug/vaccine at the correct time. The details of FBR research are presented in [Appendix 1](#).

8.4.2.1 Future Biomedical Research Sample Collection

All sample collections for study-specific assessments shown in the Schedule of Activities ([Section 1.3](#)) are described within the main informed consent.

If the participant has provided documented informed consent for FBR, leftover samples will be used for FBR. The following specimens will be included for FBR:

- Leftover samples listed in [Section 8.4.1](#)

8.5 Blood Volume Drawn for Study Assessments

Table 3: Blood Volume during the Study

Sample Type	Number of Time Points	Approximate Volume per Time Point * (mL)	Approximate Sample Volume Over Course of Study (mL)
Screening laboratory safety tests (including hematology, serum chemistry, and serology), FSH (for postmenopausal female participants only), and serum pregnancy (for female participants only)	1	12.5	12.5
Blood for planned genetic analysis	1	8.5	8.5
On-study hematology and serum chemistry (this includes serum pregnancy for female participants only when scheduled at the same time)	3	12.5	37.5
Blood for immunophenotyping	4	10	40
Blood for plasma MK-8527	16	3	48
Blood for PBMC MK-8527	12	16	192
Total Blood Volume (mL)→			338.5 **

* A smaller or larger collection tube size may be used if the present collection tube size is not available.

** If additional blood is needed for safety or PK analysis, additional blood may be collected (up to a maximum of 500 mL for the study).

9 STATISTICAL CONSIDERATIONS

Data will be handled and processed according to Celerion Standard Operating Procedures, which are written based on the principles of GCP.

9.1 Sample Size Determination

The between-participant standard deviations (on the natural log [ln] scale) for plasma MK-8527 AUC_{0-inf} and C_{max}, and for PBMC MK-8527-TP AUC_{0-inf} and C_{max} after administration of MK-8527 observed in a previous study (MK-8527-003) are 0.253 ln(h*nmol/L), 0.313 ln(nmol/L), 0.213 ln(h*pmol/10⁶ cells) and 0.262 ln(pmol/10⁶ cells), respectively. Assuming the same variability for 6 mg MK-8527, with 6 severe RI participants, 6 moderate RI participants, and 6 healthy participants, the half-width of the 90% confidence intervals (CIs) of geometric mean ratios (GMRs) for plasma MK-8527 AUC_{0-inf} and C_{max}, and for PBMC MK-8527-TP AUC_{0-inf} and C_{max} on the log scale will be 0.196, 0.242, 0.165, and 0.203 respectively. The lower and upper 90% confidence limits for the true GMRs will be given by OBS/1.21 and OBS*1.21 for plasma MK-8527 AUC_{0-inf}, OBS/1.27, and OBS*1.27 for plasma MK-8527 C_{max}, OBS/1.18 and OBS*1.18 for AUC_{0-inf} MK-8527-TP in PBMC, OBS/1.22, and OBS*1.22 for C_{max} MK-8527-TP in PBMC, where OBS is the observed least squares geometric mean ratio.

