9.3.1.3 Statistical Analyses for Plasma MK-8527 and PBMC MK-8527-TP

Separately for each PK parameter, individual values of plasma MK-8527 AUC0-last, AUC0-inf, and Cmax, of PBMC MK-8527-TP AUC0-last, AUC0-inf, Cmax, C168, and C672, after a single-dose administration of MK-8527 to participants with severe and moderate RI and to healthy control participants will be ln-transformed and evaluated with a linear fixed effects model containing a categorical effect for population (participants with severe RI, with moderate RI, and healthy control participants). An unstructured covariance matrix will be used to allow for unequal population variances via the REPEATED and GROUP statement in SAS PROC MIXED. Kenward and Roger's method will be used to calculate the denominator degrees of freedom for the fixed effect (DDFM=KR). Ninety-five percent (95%) CIs for the least-squares means (LSM) for each population will be constructed on the ln scale and will reference the t-distribution. Exponentiating the LSM and their corresponding 95% confidence limits will yield estimates for the population geometric means and CIs about the geometric means on the original scale.

Sample SAS code is given below:

```
proc mixed data=data;  
class population ;  
model lnpk = population /ddfm=kr;  
repeated/ group= population type=UN;  
lsmeans population /cl alpha=0.05;  
run;
```

To address the primary and secondary estimation objectives and compare participants with severe RI or moderate RI to healthy control participants with normal renal function, a two-sided 90% CI for the true difference in means (participants with severe RI – healthy control participants) and true difference in means (participants with moderate RI – healthy control participants) will be calculated for each PK parameter using the mean square error from the model and referencing a t-distribution. These confidence limits will be exponentiated to obtain the 90% CI for the true ratio of geometric means (participants with severe RI/healthy control participants) and (participants with moderate RI/healthy control participants) for each PK parameter.

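### The 90% CI half-widths that support 6 participants per group in Section 9.1 are about 80% half-widths; true 90% half-widths are about 31% wider on the ln scale

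*Combined protocol and SAP*

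**What the plan says.** Section 9.1 takes between-participant standard deviations on the ln scale from study MK-8527-003. For plasma AUC0-inf, plasma Cmax, PBMC MK-8527-TP AUC0-inf and PBMC MK-8527-TP Cmax, in that order, they "are 0.253 ln(h*nmol/L), 0.313 ln(nmol/L), 0.213 ln(h*pmol/10⁶ cells) and 0.262 ln(pmol/10⁶ cells), respectively". It assumes the same variability at 6 mg and a design "with 6 severe RI participants, 6 moderate RI participants, and 6 healthy participants". From this it concludes that the half-widths of the 90% intervals for the four GMRs "on the log scale will be 0.196, 0.242, 0.165, and 0.203 respectively". It then turns them into limits: "The lower and upper 90% confidence limits for the true GMRs will be given by OBS/1.21 and OBS*1.21" for plasma AUC0-inf, with factors 1.27, 1.18 and 1.22 for the other three.

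Section 9.3.1.3 defines the comparison of each renal impairment group with the healthy controls. It plans "a two-sided 90% CI for the true difference in means" for each parameter, "using the mean square error from the model and referencing a t-distribution". The same section fits a model in which each population has its own variance, with Kenward-Roger degrees of freedom.

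Section 9.3.1.5 states that no hypothesis is pre-specified. The protocol gives no power calculation.

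**The concern.** A half-width for a difference of two group means depends on three things: the SD, the group size and the t quantile. Section 9.1 gives the first two and names the confidence level, so its four figures can be checked directly. They are too small for two-sided 90% intervals with 6 per group.

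This matters because the objectives are estimation objectives. With no hypothesis and no power statement, the expected interval width is the only quantitative support for the sample size. A reader who relies on Section 9.1 will expect tighter limits on the primary plasma parameters and on the secondary PBMC parameters than this design is likely to give under its own assumptions.

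**Working it through.** **Inputs.** SDs 0.253, 0.313, 0.213 and 0.262, and 6 per group (Section 9.1). Two-sided 90% interval referring to a t-distribution (Section 9.3.1.3).

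**Formula.** Half-width = t(p, df) × SD × sqrt(1/6 + 1/6), where sqrt(2/6) = 0.57735. A two-sided 90% interval needs p = 0.95. With one variance pooled over three groups of 6, df = 18 − 3 = 15.

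**Step 1: which multiplier gives the stated figures?** Divide each stated half-width by its standard error, SD × 0.57735:

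- 0.196 / 0.14607 = 1.342
- 0.242 / 0.18071 = 1.339
- 0.165 / 0.12298 = 1.342
- 0.203 / 0.15127 = 1.342

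These agree with t(0.90, 15) = 1.341. That quantile gives 0.1958, 0.2423, 0.1649 and 0.2028, which round to all four stated values. It is the multiplier of a two-sided 80% interval. Under t with 15 df, the stated half-widths have a confidence level of 80.0% for each of the four; with 10 df it is 79%.

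**Step 2: two-sided 90% half-widths with 6 per group.** t(0.95, 15) = 1.7531 and t(0.95, 10) = 1.8125.

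| Parameter | SD | Stated half-width (factor) | 90%, 15 df | 90%, 10 df |
|---|---|---|---|---|
| Plasma AUC0-inf | 0.253 | 0.196 (1.21) | 0.256 (1.29) | 0.265 (1.30) |
| Plasma Cmax | 0.313 | 0.242 (1.27) | 0.317 (1.37) | 0.328 (1.39) |
| PBMC TP AUC0-inf | 0.213 | 0.165 (1.18) | 0.216 (1.24) | 0.223 (1.25) |
| PBMC TP Cmax | 0.262 | 0.203 (1.22) | 0.265 (1.30) | 0.274 (1.32) |

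At 15 df the ratio of correct to stated half-width is 1.307, 1.309, 1.307 and 1.306, so about 31% wider on the ln scale. At 10 df it is about 35%.

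**Step 3: does any choice of df rescue the stated values?** No. The normal quantile is the smallest multiplier available, and it gives 0.240, 0.297, 0.202 and 0.249, all above the stated values.

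**Step 4: what the separate-variance model implies.** If each group has its own variance, a contrast of two groups of 6 has at most 10 df, so the 10-df column is the most favourable case. If the df fell to 5, with the standard errors unchanged, t(0.95, 5) = 2.015 and the plasma AUC0-inf half-width would be 0.294 (factor 1.34).

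**Step 5: group size at which the stated half-widths would hold.** With pooled variance, 9 per group gives 0.204, 0.252, 0.172 and 0.211, still too wide. Ten per group gives 0.193, 0.238, 0.162 and 0.200.

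**Side note.** exp(0.196) = 1.217, which rounds to 1.22. The stated 1.21 therefore does not follow from the stated half-width; this is a separate small rounding slip.

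**The case against.** **The cause is not documented.** Section 9.1 does not name its multiplier. A genuine 90% calculation with 10 per group and two-group df, t(0.95, 18) × SD × sqrt(2/10), gives 0.196, 0.243, 0.165 and 0.203. Three of the four match, and the fourth would match if the unrounded SD lay between 0.3125 and 0.3127. Figures carried over from a larger design therefore cannot be excluded. This stands: the quantile slip is the best fit at the stated group size, but only the likely cause. The correction is the same either way.

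**Nothing reported will be wrong.** This also stands. A reader might infer that the error would carry into the results. Section 9.3.1.3 plans two-sided 90% intervals estimated from the trial's own data, and no reported interval uses the factors in Section 9.1.

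**A 2-fold margin.** A reader might set the factors against the 2-fold increase mentioned in Section 2.2.2 and infer that a conclusion shifts: with 1.21, an observed plasma AUC0-inf GMR up to 2/1.21 = 1.65 would seem to exclude a doubling, but with 1.29 only up to 2/1.29 = 1.55. The arithmetic is right, but it is illustrative only. Section 2.2.2 is a rationale for the dose; the protocol sets no decision margin there and compares no interval with that figure.

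**The df are open to reading.** Section 9.3.1.3 allows unequal variances but also bases the interval on the model's mean square error, which reads as a single pooled variance. Neither 15 nor 10 df can be called the planned value without qualification. This affects how much wider the intervals are, not whether they are wider, as Step 3 shows.

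**It is only a planning statement in a Phase 1 estimation study.** True, and no precision target is set. But expected precision is the one quantitative argument offered for the sample size, so it should be correct.

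**Conclusion.** Section 9.1 is wrong as written. With its own SDs and 6 per group, the four stated half-widths correspond to about 80% intervals. On the pooled-variance assumption (15 df), correct two-sided 90% half-widths are about 31% wider than stated on the ln scale; with separate variances the gap is about 35% at best.

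The conclusion covers the four GMRs for which Section 9.1 gives a half-width. Section 9.3.1.3 models eight parameters, and no planned precision is stated for plasma AUC0-last or for PBMC AUC0-last, C168 and C672. It rests on the printed SDs, on all 18 participants contributing data, and on the protocol's assumption that variability at 6 mg equals that in MK-8527-003.

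What is affected is the planned precision that supports the sample size. The documents do not support a claim that reported intervals would be invalid, that a decision threshold would be crossed, or that 6 per group is too few, since no required precision is specified.

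**What to change.** Keep 6 per group and restate Section 9.1:

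- Replace the half-widths with 0.256, 0.317, 0.216 and 0.265.
- Replace the limits with OBS/1.29 to OBS × 1.29 (plasma AUC0-inf), OBS/1.37 to OBS × 1.37 (plasma Cmax), OBS/1.24 to OBS × 1.24 (PBMC MK-8527-TP AUC0-inf) and OBS/1.30 to OBS × 1.30 (PBMC MK-8527-TP Cmax).
- State that these assume a variance pooled over three groups, with 15 df.
- Add that under the separate-variance model of Section 9.3.1.3 the limits are at least slightly wider. At 10 df, the most favourable case, the half-widths are 0.265, 0.328, 0.223 and 0.274, with factors 1.30, 1.39, 1.25 and 1.32. They are wider still if the Kenward-Roger df are lower.

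In the same revision, Section 9.3.1.3 should make clear whether the interval uses group-specific variances or a pooled mean square error, so that the df assumption in Section 9.1 matches the analysis.

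The cost is the rewording of one paragraph and a clarifying phrase in another. No participants are added. The stated precision becomes less favourable, and the sponsor should confirm that it is still acceptable for 6 per group.

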9.2 Population for Analyses

The following populations are defined for the analysis and reporting of data. All participants will be reported, and their data analyzed, according to the treatment(s) they actually received.

All Participants as Treated (APaT): The APaT Population consists of all participants who received the study drug. This population will be used for assessments of safety and tolerability.

Per-Protocol (PP): The PP Population consists of the subset of participants who comply with the protocol sufficiently to ensure that generated data will be likely to exhibit the effects of treatment, according to the underlying scientific model. Compliance covers such considerations as exposure to study drug, availability of measurements and absence of important protocol deviations. Important protocol deviations will be identified to the extent possible prior to database lock. Any participants or data values excluded from analysis will be identified, along with their reason for exclusion, in the CSR. At the end of the study, all participants who are compliant with the study procedure as aforementioned and have available data considered sufficient to exhibit the effect of treatment will be included in the PP dataset. This population will be used for the PK analyses.

9.3 Statistical Analyses

Detailed methodology for summary and statistical analyses of the data collected in this study will be documented in a Statistical Analysis Plan (SAP). The SAP will be prepared by Celerion and agreed upon with the Sponsor. This document may modify the plans outlined in

the protocol; however, any major modifications of the primary endpoints definition and/or its analysis will also be reflected in a protocol amendment. Additional statistical analyses other than those described in this section may be performed if deemed appropriate.

The statistical analysis of the data obtained from this study will be conducted by, or under the direct auspices of, the Early Clinical Development Statistics Department in collaboration with the Quantitative Pharmacology and Pharmacometrics Department and Translational Medicine Department of the Sponsor.

If, after the study has begun, changes are made to the statistical analysis stated below, then these deviations to the plan will be listed, along with an explanation as to why they occurred, in the Clinical Study Report.

